16.4 Description of study population

16.4.1 Demographics and baseline characteristics

Descriptive statistics for demographics, weight and height will be presented by treatment.

16.4.2 Medical/surgical history and prior/concomitant medication

Medical/surgical history and prior/concomitant medications will be presented by treatment using descriptive statistics and listings.

16.4.3 Treatment compliance

The number of subjects treated in each treatment period and their individual dose will be tabulated.

16.4.1 Physical examination

Abnormal findings will be specified and presented by subject and summarised by treatment and period.

16.4.2 Safety laboratory analyses

Safety laboratory data will be presented by individual time courses for each parameter and subject and summarised by treatment and period.

16.5 Analysis of primary endpoints

16.5.1 Comparison of total nicotine exposure (AUC_{inf}) after administration of ZYN[®] 6mg and 2 pouches of 8 mg Swedish snus

AUC_{inf} based on plasma concentrations of nicotine after administration of one single dose of ZYN® Smooth 6 mg of nicotine, to that of one single dose 2 pouches of 8mg Swedish snus will be described using summary statistics and non-parametric signed Wilcoxon rank sum test for between treatment difference.

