8.5 Number of subjects

36 subjects will be included in the study.

For replacements of subjects discontinuing the study, see Section 8.5.

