8.11 Randomization

On study Day 1 (Visit 2), the subjects will be randomised to a treatment sequence. As this is an open study, the treatments to which each subject is allocated for the first dose administrations will be recorded in the eCRF. A computer-generated randomisation list will be created using SAS Proc Plan, SAS Version 9.4. The randomisation list will contain subject number, treatment sequence, period, and treatment.

The randomisation list will be generated by CTC or delegate and provided to the packing company. The original randomisation list will be kept by the randomiser. A copy of the randomisation list will be provided to the clinic. A coded copy of the randomisation list will be generated, i.e. a list where the treatment is blinded and this coded list will be provided to the bioanalytical laboratory and to the pharmacokineticist.

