16.1 General

Pharmacokinetic data will be presented using summary statistics. Data will be presented in terms of number (N), arithmetic mean, standard deviation (SD), median, minimum and maximum value. In addition, for the parameters AUC and C_{max} the geometric mean and coefficient of variation (CV) will be presented.

Categorical data will be presented as counts and percentages. When applicable, summary data will be presented by treatment, and by assessment time. Individual subject data will be listed by subject number, treatment, and, where applicable, by assessment time.

The primary endpoint will be investigating a one sided hypothesis that ZYN 6mg has a lower AUC compared to 2 pouches of 8 mg Swedish snus, using a significance level of 2.5%. All other test will be two-sided with a significance level of 5%.

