16.6 Analysis of secondary endpoints

16.6.1 Comparison of PK profiles between all included products

The PK analysis will be based on the PPAS and performed by CTC. The PK parameters will be calculated by non-compartmental analysis (NCA) using the software Phoenix WinNonlin® version 6.3 or later (Pharsight Corporation, U.S.A.).

The following non-compartmental PK parameters will be assessed:

- T_{max} (sampling time at which C_{max} occurred)
- C_{max} (maximum observed concentration)

- AUC_{inf} (area under the curve from 0 to infinity)
- AUC_{last} (area under the curve from 0 to t hours where t is the last measured concentration)

The mean + SD of AUCinf based on plasma concentrations of nicotine after administration of each pouch, will be calculated. AUC_{0-t}, AUC_{inf}, Cmax, Tmax, and terminal half-life will also be calculated.

AUC_{0-t}, AUC_{inf}, Cmax, Tmax, and terminal half-life of all included products will be described using summary statistics and analyzed using signed Wilcoxon rank sum test for between treatment differences for all pairwise comparisons.

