16.6.2 In-vivo extracted amount of nicotine

The mean + SD extracted dose of nicotine from each pouch, will be calculated. The extracted dose of nicotine will be analyzed using the signed Wilcoxon rank sum test for within subject difference.

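### The primary test is named ambiguously (paired or unpaired), leaves out the randomised period, and yields a p-value with no between-product ratio or confidence limit

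*Protocol*

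**What the plan says.** The primary comparison in section 16.5.1 is made by "summary statistics and non-parametric signed Wilcoxon rank sum test for between treatment difference". Section 16.6.1 applies the same test to AUC0-t, AUCinf, Cmax, Tmax and terminal half-life, as "signed Wilcoxon rank sum test for between treatment differences for all pairwise comparisons". Section 16.6.2 uses the same name for extracted nicotine, but there as a "signed Wilcoxon rank sum test for within subject difference".

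Section 16.1 words the primary hypothesis thus: "one sided hypothesis that ZYN 6mg has a lower AUC compared to 2 pouches of 8 mg Swedish snus, using a significance level of 2.5" per cent. It lists per-product summaries, including geometric mean and CV for AUC and Cmax. No section specifies a between-product ratio, a difference estimate or a confidence interval.

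The trial is a seven-way crossover in which subjects are randomised to sequences. Under section 8.11, "The randomisation list will contain subject number, treatment sequence, period, and treatment". No PK comparison has a period term.

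Section 16.2 gives AUCs of 3581 and 5586, a common SD of 1920, 80% power and a 2.5% level, and arrives at 32 subjects, or 36 with 10% dropout. Section 6.2 states the aim: ZYN products should not give higher nicotine exposure than marketed snus-type products.

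**The concern.** Three things are fixed badly in the protocol text itself.

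1. The test name does not identify one test. The signed-rank test works on within-subject differences; the rank-sum test treats the two sets of values as independent groups. Two programmers could run different primary tests and both claim compliance. The same name governs the secondary PK comparisons: 7 × 6 / 2 = 21 product pairs, times 5 parameters, is 105 tests.

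2. Period is built into the randomisation but absent from the analysis, so any drift over about 7 weeks stays in the product differences as noise.

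3. A p-value does not say how much lower the exposure is or how much higher it could still be. This matters most for secondary pairs such as ZYN 8 mg or ZYN against Longhorn, where a non-significant two-sided test cannot show that exposure is not higher.

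**Working it through.** **Reproducing the plan's figure.** Inputs from section 16.2: difference 5586 − 3581 = 2005, SD 1920, one-sided 2.5%, power 80%.

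- Two independent groups, normal approximation: n per group = 2 × (1.960 + 0.842)² × (1920/2005)² = 2 × 7.849 × 0.917 = 14.4, so 15 per group and 30 in all.
- Two independent groups, exact t-test: 15.4, so 16 per group and **32 in all**, as stated. Dropout: 32 / 0.90 = 35.6, so **36**, as stated.
- Paired t-test, 1920 taken as the SD of differences: 9.3, so 10 pairs.
- Paired t-test, 1920 taken as the SD within each product: the SD of differences is 1920 × √(2(1 − ρ)). The correlation ρ is not in the protocol, so a range is assumed.

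| Assumed ρ | SD of differences | Pairs needed | Power with 32 pairs | Unpaired / paired variance, 1/(1 − ρ) |
|---|---|---|---|---|
| 0 | 2715 | 17 | 98% | 1.0 |
| 0.25 | 2352 | 13 | 99.7% | 1.33 |
| 0.50 | 1920 | 10 | >99.9% | 2.0 |
| 0.75 | 1358 | 6 | >99.9% | 4.0 |

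Of the calculations tried, only the unpaired one gives 32. Section 8.2 (each subject as own control) and section 16.6.2 (within-subject difference) point to pairing. The last column shows what choosing the wrong test could cost.

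**Does leaving out period make the paired test invalid?** Simulation: 32 subjects, random orders, assumed linear drift of 0 to 2000 AUC units across the seven periods, assumed ρ of 0 or 0.5, 3000 runs per setting. The paired signed-rank test kept its one-sided type I error at 2.2% to 2.9% (nominal 2.5%). Power was 96% to 97% at ρ = 0 and above 99% at ρ = 0.5. So it stays valid.

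**What does it cost in precision?** Assume a within-subject log SD of 0.30 and independent period effects with SD 0.20. With unrestricted random orders, the variance of one subject's product difference is:

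- without period effects: 2 × 0.30² = 0.18
- with period effects: 0.18 + 2 × 0.20² = 0.26
- ratio: 0.26 / 0.18 = 1.44, before the small cost of adjustment. Simulation of the seven-product model gives about 1.4.

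With Williams sequences in blocks of 14, 36 randomised and 4 random dropouts, the simulated ratio is only about 1.1. At a period SD of 0.30 the ratios are about 1.8 to 2.0 (closed form 0.36 / 0.18 = 2.0) and about 1.2.

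The reason lies in how evenly products spread over periods. With random orders, the gap between two products' periods has variance 8 + 8/6 = 9.33 per subject, so the mean gap over 32 subjects has SD √(9.33/32) = 0.54 periods. With Williams sequences the simulated SD is 0.24.

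With no period effect, the unadjusted/adjusted variance ratio is 0.96 under random orders. Adjustment then costs √(1/0.96) = 1.02, about 2% in SE.

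**The case against.** The strongest defence is that context settles the name: only the paired test is signed, section 16.6.2 speaks of within-subject differences, and the PK set consists of completers. Much of that stands, and pairing is the more natural reading. But the sample size points the other way, and a primary test should not have to be inferred.

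A reader might infer that ignoring period biases the primary result, inflates its error rate or threatens its power. The documents do not support this: order is randomised, the simulated type I error holds, and 32 pairs give at least 98% power by paired t-test even at ρ = 0. A particular list may by chance place one product later than another, but that is a conditional imbalance, not bias on average.

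A reader might also take the 1.4-fold variance as the expected loss. It applies only to unrestricted random orders and the assumed SDs. Section 8.11 does not say how sequences are formed, and a balanced set brings the figure to about 1.1.

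That 36 is not a multiple of 7 carries little weight: 35 subjects fill five complete sets, and dropout would break exact balance at any number.

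Finally, an analysis plan that is not shown could add a confidence interval, and the planned geometric means already allow a point ratio. So the missing interval is weak taken alone. It counts because the protocol fixes a test-only comparison for an aim about the size of exposure. Adding period would mean departing from the stated test.

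**Conclusion.** The point holds as one of specification, precision and interpretation, and the protocol should be changed. The test name is ambiguous in all three analysis sections, and the sample size contradicts the paired reading that the design implies.

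A paired signed-rank test would be valid and well powered. What is lost is some precision (variance about 1.1 to 1.4 times larger at an assumed within-subject log SD of 0.30 and period SD of 0.20, depending on how sequences are drawn; negligible without a period effect) and an estimate with a limit that speaks to the aim. The protocol gives neither of those SDs, nor the within-subject correlation.

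**What to change.** Make the primary analysis a linear mixed model on log AUCinf, all seven products in one model, with product and period as fixed effects and subject as random effect. Add sequence only if a limited set of sequences is used. With unrestricted orders there are 7! = 5040 possible sequences, and all 36 subjects would have different ones with probability about 0.88, so sequence could not be separated from subject.

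Report the ZYN Smooth 6 mg / General geometric mean ratio with a two-sided 95% CI. Success is an upper limit below 1, which keeps the one-sided 2.5% level. Use the same model for AUC0-t, Cmax and extracted amount. Name the paired Wilcoxon signed-rank test explicitly for Tmax and as the sensitivity analysis.

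The cost is rewording sections 16.5.1 and 16.6 and minor programming, with no new subjects, visits or data. The model assumes approximate log-normality and costs at most about 2% in SE if there is no period effect.

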16.6 Analysis of secondary endpoints

16.6.1 Comparison of PK profiles between all included products

The PK analysis will be based on the PPAS and performed by CTC. The PK parameters will be calculated by non-compartmental analysis (NCA) using the software Phoenix WinNonlin® version 6.3 or later (Pharsight Corporation, U.S.A.).

The following non-compartmental PK parameters will be assessed:

- T_{max} (sampling time at which C_{max} occurred)
- C_{max} (maximum observed concentration)

- AUC_{inf} (area under the curve from 0 to infinity)
- AUC_{last} (area under the curve from 0 to t hours where t is the last measured concentration)

The mean + SD of AUCinf based on plasma concentrations of nicotine after administration of each pouch, will be calculated. AUC_{0-t}, AUC_{inf}, Cmax, Tmax, and terminal half-life will also be calculated.

AUC_{0-t}, AUC_{inf}, Cmax, Tmax, and terminal half-life of all included products will be described using summary statistics and analyzed using signed Wilcoxon rank sum test for between treatment differences for all pairwise comparisons.

16.6.2 In-vivo extracted amount of nicotine

The mean + SD extracted dose of nicotine from each pouch, will be calculated. The extracted dose of nicotine will be analyzed using the signed Wilcoxon rank sum test for within subject difference.

16.6.3 Correlation between extracted nicotine and AUCinf

The correlation between the AUC and the total amount of nicotine extracted from the pouch will be analyzed using Proc corr. in SAS.

16.6.4 Analysis of plasma levels of Methyl salicylate

Plasma levels of Methyl salicylate will be summarized using descriptive statistics.

16.6.5 Adverse events

AE data will be summarised by System Organ Class (SOC) and PT. All AE data will be fully listed and include the verbatim term entered by the Investigator.

